4.2. Study Endpoints

4.2.1. Primary Endpoints

- Safety and tolerability of each column size and each blood-flow rate.
 - Evaluation of safety and tolerability will include assessment of the rate and severity of all AEs, with analyses of ADEs, TEAEs, number of IDH events, and changes in total and free Hgb.
 - O Tolerability will be assessed by the proportion of subjects who can escalate to and tolerate each column size and blood-flow-rate combination.

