15.3. Schedule of Laboratory Tests

Assessment	Screening	I	Run-i	n									Treat	tment]	Period								End of Study (EOS)
	V1	V2	V3	V4	V5	V6	V7	V8	V9	V10	V11	V12	V13	V14	V15	V16	V17	V18	V19	V20	V21	V22 (EOT)	V23
b2M/proteomics				X			X			X			X			X			X			X	X
Serum pregnancy (WOCBP only)	X			X																			X
Hematology						Note	: CBC	, Hp, I	Hgb, aı	nd plasr	na-free l	Hgb sho	uld be ta	aken AI	TER H	D V4-V	21.						
Complete blood count (CBC)	X					X			X									X			X		
Haptoglobin (Hp)				X		X			X									X			X		
Hemoglobin (Hgb)	X					X			X									X			X		X
Plasma-free Hgb				X		X			X									X			X		
Chemistry			Note	: BUN	and (Creatin	ine sh	ould b	e colle	cted BE	FORE a	and AFT	ER HD										
Alanine aminotransferase (ALT)	X											X											
Albumin	X											X											
Aspartate transaminase (AST)	X											X											
Bicarbonate (HCO ₃)	X											X											
Bilirubin (total)	X											X											
Blood urea nitrogen (BUN)	X		X			X			X			X			X			X			X		
Calcium (Total)	X						X															X	
Chloride (Cl)	X											X											
Creatine kinase (CK)	X																						
Creatinine	X		X			X			X			X			X			X			X		
Glucose	X						X					X										X	
Hemoglobin A1c (HbA1c)	X																						

Protocol AKST1210-101 V2.1 13MAY2021

Assessment	Screening	I	Run-ii	n									Treat	ment l	Period								End of Study (EOS)
	V1	V2	V3	V4	V5	V6	V7	V8	V9	V10	V11	V12	V13	V14	V15	V16	V17	V18	V19	V20	V21	V22 (EOT)	V23
Lactate dehydrogenase (LDH)	X																					(= 0 = 7	
Magnesium (Mg)	X																						
Potassium (K)	X											X											
Phosphate	X											X											
Protein (total)	X											X											
Sodium (NA)	X											X											
Coagulation																							
Activated partial thromboplastic time (aPTT)	X											X											
Prothrombin time (PT/INR)	X											X											
Serology																							
Hepatitis B surface/core antigen (HBsAg)	X																						
Hepatitis C antibody (HCV Ab)	X																						
Human immunodeficienc y virus antibody (HIV Ab, HIV1/HIV-2)	X																						
Other Clinical Labs	Note: All la section should						Note	: All la	ıbs in 1	he "Otl	ner Clini	cal Labs	s" sectio	n shoul	d be col	lected E	BEFORE	E and A	FTER H	D at V7	and V2	.22.	
Adrenocorticotro pic hormone (ACTH)				X			X															X	
Complement (total)(CH50)				X			X															X	
Complement C3 and C4				X			X															X	
Complement C5a				X			X															X	

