17.1.2. De-escalation Rules

The purpose of the de-escalation rules is to ensure the safety of a subject who is experiencing IDH, anemia or other safety issues that may be related to the column size.

A subject should be de-escalated if during the 1-week treatment period they experience the number of IDH events described in the table above and/or have an Hgb level < 9 g/dL despite receiving optimized treatment with ESA.

De-escalation will only be applicable at V11 through V19 as shown in Figure 4 below. Subjects who do not tolerate treatment with the S-15 column at any time prior to V11 or after V19 will be discontinued (see Section 17.1.13. Discontinuation Rules).

Figure 4. De-escalation Schematic

Subjects will continue with the same visit schedule after de-escalation. At the visit following confirmation of de-escalation, treatment will resume with the previous column size at the high flow rate (up to 450 mL/min).

- ➤ If de-escalation occurs during V11 through V16, subjects will resume treatment at the next scheduled visit with the S-15 column at up to 450 mL/min and will continue with this column size/flow rate combination through EOT (V22).
- ➤ If de-escalation occurs during V17 through V19, subjects will resume treatment at the next scheduled visit with the S-25 column at up to 450 mL/min and will continue with this column size/flow rate combination through EOT (V22).

Table 4 below illustrates the visit schedule for subjects who de-escalate. *Note*: the only change compared to Section 15 is column size and flow rate.

Table 4. Schedule of Events for Subjects Who De-escalate

					,	Treatm	ent Peri	iod					EOS
Visit Number	V11	V12	V13	V14	V15	V16	V17	V18	V19	V20	V21	V22 (EOT)	V23
Study Week		Week 3			Week 4	ļ	,	Week 5			Week	6	Week 7
Study Day(s) (± 1)	Day 15	Day 17	Day 20	Day 22	Day 24	Day 27	Day 29	Day 31	Day 34	Day 36	Day 38	Day 41	Day 43
Procedure													
Physical examination													X
12-lead ECG													X
Targeted physical examination	X	X	X	X	X	X	X	X	X	X	X	X	
Weight	X	X	X	X	X	X	X	X	X	X	X	X	X
Vital signs ¹	X	X	X	X	X	X	X	X	X	X	X	X	X
Laboratory tests ²		X	X		X	X	X	X	X	X		X	X
Column size			S-	15			S-15	OR S-2	.5 (if de	e-escala	ated aft	er V16)	
Hemodialysis blood-flow rate (mL/min)						Up	to 450						
Assessment of fluid status	X	X	X	X	X	X	X	X	X	X	X	X	
Kt/V assessment		X			X		_	X			X	X	_
Adverse events and concomitant medications	X	X	X	X	X	X	X	X	X	X	X	X	X

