2.3 Primary Endpoint

- Safety and tolerability of each column size and each blood-flow rate.
 - Evaluation of safety and tolerability will include assessment of the rate and severity
 of all treatment emergent adverse events (TEAEs), with analyses of adverse device
 effects (ADEs), number of intradialytic hypotensive (IDH) events, and changes in
 total and free hemoglobin (Hgb).
 - O Tolerability will be assessed by the proportion of subjects who can escalate to and tolerate each column size and blood-flow-rate combination.

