4.1 General Considerations

This section presents the statistical approaches that are anticipated for the analysis of the study data. These approaches may at times require modifications due to unanticipated features of the data. Deviations from analyses summarized in this document will be noted in the CSR.

All statistical analyses will be performed using SAS® Version 9.4 or higher, unless otherwise noted.

Data from this feasibility study will be analyzed mostly in a descriptive manner. Limited statistical comparison of outcomes across the various column-size and blood-flow-rate combinations will be performed. Details for any statistical tests are provided in the endpoint analysis sections (4.7, 4.8).

All safety endpoints will be summarized descriptively and tabulated as necessary, unless otherwise stated. Overall baseline and demographic data will be summarized using descriptive statistics.

For analysis of the primary and secondary endpoints, the following will be considered:

- For endpoints that are continuous in nature:
- Number of observations, mean, median, minimum and maximum, and standard deviation (SD) and change from baseline values (or percent change from baseline) will be presented as descriptive summary.
- For endpoints that are categorical in nature:
- Frequency counts and percentages will be presented as descriptive summaries.

Descriptive statistics will be utilized for trial conduct: screen failures, enrollment, withdrawal of consent, and study completion. Primary and secondary endpoints will be assessed at the beginning and end of each week of treatment for a particular column size and blood-flow rate combination. The effect of blood-flow rate will be assessed for a given column size as well as intrasubject and across-subject variability. The sample size was chosen based on clinical consideration of the study designed to test the safety and functionality of the column operated at higher blood-flow rates (up to 450 mL/min).

In general, all summary tables will be supported by a relevant subject data listing. The listings will include all data collected, and will be sorted by subject ID, and actual visit date, as applicable, unless otherwise noted. The listing will also include the column size and blood-flow rate combination as applicable.

Study day 1 is the first day of HD treatment with the day relative to the study day 1.

Statistical Analysis Plan AKST1210-101

Rev. A Page 12 of 28

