Baseline is the first value after the start of HD with the column. For the assessments that do not take place during the treatment weeks (e.g., ECG, physical examination, etc.), the value from Screening will be the baseline. Baseline for lab values will be the last non-missing value prior to the start of HD with the column.

Change from baseline is the post-treatment value minus baseline value.

Subjects who de-escalate (i.e., do not proceed to the next column size and blood-flow rate combination) will only be included in analysis up to the point of de-escalation.

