4.6 Methods for Handling Missing Data

No imputation of missing data will be performed.

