4.7.3 Change in Total and Free Hemoglobin

Plasma levels of total Hgb and free Hgb at baseline (i.e., the last nonmissing value prior to the start of HD with the column) and each scheduled post-baseline timepoint, along with change from baseline at each scheduled post-baseline timepoint will be summarized for the Safety, Evaluable and PP populations, by each column size and blood-flow rate combination and total.

A listing of total and free Hgb level, as well as the changes from baseline at each scheduled post-baseline timepoint will be provided.

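### Change in total and free hemoglobin is part of the primary endpoint for every column and flow-rate combination, but neither S-25 combination has a scheduled hemoglobin sample

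*SAP*

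**What the plan says.** Protocol 4.2.1 lists among the primary safety and tolerability measures the "number of IDH events, and changes in total and free Hgb", to be evaluated for each column size and blood-flow rate. SAP 2.3 repeats this. SAP 4.7.3 plans observed values and changes from baseline at the scheduled time points; these "will be summarized for the Safety, Evaluable and PP populations, by each column size and blood-flow rate combination and total". SAP 4.9.5 takes the laboratory time points from Protocol 15.3.

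SAP 4.1 adds a comparison: "The effect of blood-flow rate will be assessed for a given column size as well as intrasubject and across-subject variability".

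Three other provisions decide whether missing values could be recovered:

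- SAP 4.6: "No imputation of missing data will be performed".
- SAP 4.1: subjects who de-escalate "will only be included in analysis up to the point of de-escalation".
- Protocol 7.1.1.2.5 and 7.2: local laboratory testing is allowed at the investigator's discretion, for ad hoc safety monitoring or heparin dosing.

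**The concern.** The schedule in Protocol 15.3 appears to skip hematology for the whole of Weeks 3 and 4, the two S-25 weeks. If so, the S-25 columns of a primary-endpoint table would be empty from scheduled data, and for this component the middle column size would drop out of both the flow-rate and the size comparisons.

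There is a linked point. Protocol 17.1.1 and 17.1.2 use an Hgb criterion for escalation and de-escalation, and SAP 4.7.4 tabulates anemia as a reason for de-escalation. In the S-25 weeks no scheduled Hgb value would stand behind either.

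**Working it through.** The plan states no figure of its own for Hgb sampling, so the check is a count of the marks in Protocol 15.3 against the visit windows in the Protocol Summary and SAP 3.1. Each row of the grid has 23 visit cells, V1 to V23.

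**Marks by row**

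- Total Hgb: V1, V6, V9, V18, V21, V23.
- "Plasma-free Hgb" and haptoglobin: V4, V6, V9, V18, V21.
- CBC: V1, V6, V9, V18, V21.
- BUN, as an alignment check: V1, V3, V6, V9, V12, V15, V18, V21.

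**Marks by combination**

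| Combination | Visits | Total Hgb | Free Hgb | BUN |
|---|---|---|---|---|
| S-15, 250 mL/min | V5-V7 | V6 | V6 | V6 |
| S-15, up to 450 mL/min | V8-V10 | V9 | V9 | V9 |
| S-25, 250 mL/min | V11-V13 | none | none | V12 |
| S-25, up to 450 mL/min | V14-V16 | none | none | V15 |
| S-35, 250 mL/min | V17-V19 | V18 | V18 | V18 |
| S-35, up to 450 mL/min | V20-V22 | V21 | V21 | V21 |

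A fault in reading the table is unlikely. All four hematology rows share the same gap, while BUN and creatinine in the same grid are marked at V12 and V15. The general laboratory marks at V12, V13, V15 and V16 in Protocol 15.2 are explained by BUN, creatinine and other non-hematology tests (V12, V15) and by b2M (V13, V16).

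**Size**

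- Combinations with no scheduled value: 2 of 6.
- Column sessions with hematology: 4 of 18 (V5-V22). Of the 18 - 4 = 14 without, 6 are all of the S-25 sessions.
- Subject-by-combination cells without a value: 12 × 2 = 24 of 12 × 6 = 72 if 12 subjects complete; 15 × 2 = 30 of 15 × 6 = 90 if 15 do.
- Flow-rate comparisons within a size: 1 of 3 is lost. Size comparisons within a flow rate: 3 pairs × 2 rates = 6, of which the 2 × 2 = 4 that involve S-25 are lost. Together, 5 of 9.
- Gap between scheduled values: V9 (Day 10) to V18 (Day 31) = 21 days, or 19 to 23 with the ±1-day windows, with 8 sessions (V10-V17) in between.
- Escalation steps occur at V8, V11, V14, V17 and V20. The week just completed holds V6, V9, none, none and V18, so 2 of 5 steps have no scheduled Hgb behind them.

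**Could the values come from elsewhere?** Discretionary local tests are not scheduled time points. Nothing is imputed. If de-escalation occurs during V17-V19, "subjects will resume treatment at the next scheduled visit with the S-25 column at up to 450 mL/min", so a V18 or V21 sample could fall on S-25. SAP 4.1 ends that subject's analysis at de-escalation, so the value would appear in a listing only.

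**Total-Hgb baseline (minor).** The only total Hgb in the grid before column use is at V1, taken on a non-dialysis day or before dialysis (Protocol 7.1.1.1.5). The V6-V21 values are taken after dialysis. If Hgb moved by a fraction r over a session, an unchanged 10.0 g/dL would show a change of 10(1 + r) - 10: 0, +0.5, +1.0 or +1.5 g/dL for assumed r of 0, 5, 10 or 15%, with the sign reversed for a fall. Neither size nor direction is in the documents. Free Hgb is unaffected, since it has a post-dialysis V4 value.

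**The case against.** The strongest reply is that the sparse schedule is deliberate and the SAP wording merely generic. SAP 4.7.3 refers to scheduled time points, and the SAP defers to Protocol 15.3 for them. SAP 4.8.6 also promises summaries by combination for other proteins that are drawn during column use only at V7 and V22. Sampling the smallest and largest columns is a reasonable economy, since S-25 lies between them in capacity and extracorporeal volume (65, 105 and 177 mL in Protocol Table 2). This may be the explanation, but the documents do not say so. SAP 4.8.6 names its limited visits openly; SAP 4.7.3 does not. Even if intended, the plan promises six combinations and can deliver four.

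It is also fair that one draw per week is no defect in itself, so the 14 of 18 sessions should not be read as a failing, and that the plan specifies no list of Hgb contrasts. The figure that matters is 2 of 6, plus the one within-size flow comparison that SAP 4.1 promises and S-25 cannot provide.

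On the Hgb criterion, Protocol 17.1 does not require a value drawn under 15.3, and local testing could supply one. That makes it a gap in specification more than a direct contradiction, but the source of the value is still unstated. The note in 15.3 placing CBC and Hgb after dialysis from V4 to V21 can likewise be read as a timing instruction that adds no visits. It still names V4 as the start of the range, and the grid has no V4 mark for either test.

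**Conclusion.** The concern holds. From scheduled values, the Hgb part of the primary endpoint cannot be summarized for S-25 at either flow rate: 2 of 6 combinations are empty, and comparison by size reduces to S-15 against S-35. This rests on a count of the printed grid and on no statistical assumption; the cell counts assume that 12 to 15 subjects enter every combination.

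The consequence is moderate. Adverse events, intradialytic hypotension and tolerability are still recorded in the S-25 weeks, Hgb is measured on the smallest and largest columns at both flow rates, and the study is descriptive. It should be fixed because a primary-endpoint component is affected and the remedy is simple. The baseline point is minor: a common shift largely cancels between combinations.

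**What to change.** Preferred: amend Protocol 15.3 to add post-dialysis CBC/Hgb, haptoglobin and plasma-free Hgb at V12 and V15. Both visits already have a post-dialysis BUN draw. Every combination then has one scheduled value (6 of 18 sessions, 6 of 6 combinations). The cost is a schedule amendment and 2 × 12 = 24 to 2 × 15 = 30 extra sample sets. Adding post-dialysis CBC/Hgb at V4 (12-15 more samples) would give total Hgb a baseline with matching timing and bring the grid into line with its note.

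If no draws are added: restate the Hgb endpoint and SAP 4.7.3 as covering S-15 and S-35 only, note that changes in total Hgb from V1 mix sample timing with any column effect, and correct the 15.3 note or grid. This costs wording only.

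In either case, state in SAP 4.7.4 the source and date of the Hgb value behind an anemia de-escalation, and reconcile Protocol 15.3 with the Hgb criterion in 17.1.1 and 17.1.2; no clinical rule is proposed here. Separately, the list of combinations in SAP 4.7 omits S-35 at 250 mL/min, which SAP 4.8 includes, and should be corrected.

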4.7.4 Tolerability of each Column Size and Blood-flow-rate Combination

The number and percentage of subjects will be summarized for the Safety, Evaluable and PP populations, by each column size and blood-flow rate combination and total for the following:

- Subjects entered each column size/blood-flowrate combination
- Subjects who de-escalated to a lower column size categorized by reason: IDH, anemia, or other. Anemia (as it pertains to de-escalation) is defined as having an Hgb lab value of < 9 g/dL despite receiving optimized treatment with erythropoietin stimulating agents (ESA).
- Subjects who were discontinued due to safety, tolerability, and/or investigator discretion
- Subjects who completed all the visits

4.8 Secondary Analyses

Secondary analyses include HD parameters, thrombosis events, weight, b2M, complement factors, and other plasma protein levels. Except where indicated, secondary endpoints will be summarized by each column size and blood-flow rate combination (S-15 250mL/min, S-15 up to 450 mL/min, S-25 250mL/min, S-25 up to 450 mL/min, S-35 250mL/min, S-35 up to 450 mL/min) using both Safety and Evaluable populations.

4.8.1 Hemodialysis Parameters

Kt/V and URR (%) will be summarized for the Safety, Evaluable and PP populations, by visit and each column size/flow-rate combination.

Kt/V will be calculated with Daugirdas' formula from the pre-dialysis to post-dialysis urea nitrogen ratio (R), the weight loss (UF), session length in hours (t), and anthropometric or modeled volume (V) using the equation: $Kt/V = In (R - 0.008 \times t) + (4 - 3.5 \times R) \times 0.55 \text{ UF/V}$ (Daugirdas 1995).

URR (%) is calculated as:

URR (%) = (1 - post-dialysis BUN / pre-dialysis BUN) * 100

For evaluation of total fluid balance, the initial fluid removal goal (mL), actual fluid removal (mL), and amount differs from the goal will be summarized by column size and blood-flow rate combination.

Actual fluid removal is calculated as follows: Weight (kg) – Weight Post-Dialysis (kg) and subsequently converting weight to volume (1 kg = 1000 mL).

In addition, the number and percent of subjects who achieved the dry weight goal (i.e., Weight Post-Dialysis (kg) is less than or equal to Estimated Dry Weight) will be summarized by column size and blood-flow rate combination.

A listing of HD parameters will be provided. Other HD parameters will not be summarized but will be provided in the listing only.

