The duration of each HD treatment will be adjusted to ensure adequate Kt/V with a reduced flow rate (approximately 4-6 hours at 250 mL/min, 3-4 hours at up to 450 mL/min). During each week determination of HD adequacy will include KtV > 1.2 (calculated from measurements of blood urea) and urea reduction ratio (URR) (weekly URR > 65%).

The most important known potential risk for use of the column is an increased risk of IDH. Risk mitigations may include prophylactic administration of saline, supine positioning/lower limb elevation, avoidance of fasting before HD, avoidance of food intake during HD, use of cooled dialysate, education about the importance of avoiding excessive fluid gain between HD sessions (interdialytic weight gain), and avoiding the use of ultrafiltration rates (UFR) above 13 mL/kg/h. Concomitant medications, especially medications related to or affecting blood pressure (BP), should remain stable while on study and receiving HD with the

The occurrence of IDH events during each week, as outlined in Appendix 17.1: Escalation, De-escalation, and Discontinuation Rules for Treatment with the Column, will be one factor used to determine column size/blood-flow rate escalation/de-escalation as well as discontinuation from the study. There is also a possibility that the blood-flow rate of 450 mL/min cannot be attained due to factors related to the dialysis circuit or other technical issues. If the blood-flow rate of 450 mL/min cannot be attained, it can be adjusted down to enable continued dialysis at a blood-flow rate as high as possible. The reason(s) for the inability to attain a blood-flow rate of 450 mL/min must be documented.

Endpoints:

Primary Endpoints:

- Safety and tolerability of each column size at each blood-flow rate.
 - Evaluation of safety and tolerability will include assessment of the rate and severity of all adverse events (AEs), with analyses of adverse device effects (ADEs), treatment-emergent AEs (TEAEs), number of IDH events, and changes in total and free hemoglobin (Hgb).
 - Tolerability will be assessed by the proportion of subjects who can escalate to and tolerate each column size and blood-flow-rate combination.

Secondary Endpoints

- Weekly Kt/V and URR.
- Total fluid balance for each column-size flow-rate combination.
- Proportion of subjects who are able to achieve the dry weight goal during the allotted HD duration for each column size and flow rate combination.

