The duration of HD time will be adjusted for flow rate (approximately 4-6 hours for 250 mL/min, 3-4 hours for up to 450 mL/min). During each HD session, measurements of HD effectiveness will include Kt/V>1.2 (calculated from measurements of blood urea) and URR (weekly URR >65%).

The mean and max blood flow rate will be calculated/pulled from the entries on the HDE CRF rather than the HD CRF.

The incidence of IDH events, as defined in Protocol Appendix 17.1: Escalation, Deescalation, and Discontinuation Rules for Treatment with the Column, will be one factor used to determine column size/blood-flow rate escalation/de-escalation as well as discontinuation from the study.

The planned duration of subject participation is approximately 12 weeks (up to 4 weeks for screening and 8 weeks on-study, which is inclusive of the 1-week run-in period).

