4.4 Demographics and other Baseline Characteristics

4.4.1 Demographics

Sex, women of childbearing potential (WOCBP), age (in years), race, ethnicity, baseline BMI (kg/m²), and subjects' highest education level will be summarized by column size and blood-flow rate combinations, and Total, for the Safety population. BMI (kg/m²) will be calculated as: 10,000*weight (kg) / the square of height (cm). If height is collected in inches, it will be converted to cm by dividing the value by 2.54. If weight is collected in pounds, it will be converted to kg by dividing the value by 2.205.

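### SAP 4.8.1 defines R as the pre/post urea ratio, which does not fit its Kt/V equation: used literally, Kt/V is under-reported and falls as more fluid is removed

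*SAP*

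**What the plan says.** SAP 4.8.1 builds Kt/V "from the pre-dialysis to post-dialysis urea nitrogen ratio (R), the weight loss (UF), session length in hours (t") and a volume V described as anthropometric or modeled. The equation starts "using the equation: $Kt/V = In (R - 0.008" (the log printed as In) and in full reads Kt/V = ln(R − 0.008t) + (4 − 3.5R) × 0.55 UF/V.

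The same section defines the companion measure the other way up: "URR (%) = (1 - post-dialysis BUN / pre-dialysis BUN) * 100".

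Both documents pair two adequacy thresholds; in SAP 3.1, "measurements of HD effectiveness will include Kt/V>1.2 (calculated from measurements of blood urea) and URR (weekly URR >65"%). Planned session length differs by flow rate: "approximately 4-6 hours for 250 mL/min, 3-4 hours for up to 450 mL/min".

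Kt/V is a secondary endpoint (SAP 2.4), summarized by visit and column-size/flow-rate combination in three populations. The protocol names the same formula but prints no equation and does not define R, so nothing there corrects the SAP.

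A separate slip is in SAP 4.4.1: "If height is collected in inches, it will be converted to cm by dividing the value by 2.54".

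**The concern.** The words and the equation cannot both be right. A positive log suits R = pre/post. The terms −0.008t and (4 − 3.5R) suit R = post/pre, because only then does a longer session or more fluid removal add to the clearance. As written, fluid removal counts against Kt/V.

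Three things follow if this is programmed literally:

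- Kt/V tables would show values below 1.2 for sessions whose URR meets the plan's own threshold.
- The error grows with fluid removal, so it is not a constant offset.
- The error also depends on session length, which the design ties to flow rate, so it does not cancel from the flow-rate comparison.

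On the positive-log reading the wrong values look plausible, so they could reach the report unnoticed.

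**Working it through.** **Inputs.** From the documents: the equation, the definition of R and the URR formula (SAP 4.8.1); the thresholds of 1.2 and 65%; t = 3 to 6 h. The documents give no worked Kt/V value to reproduce, and no figures for UF or V.

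**Assumption for fluid.** Write f = 0.55 UF/V. If V is 55% of body weight, f is fluid removed as a share of body weight. I take f = 0 to 5%. As a benchmark, the protocol summary lists among its mitigations "avoiding the use of ultrafiltration rates (UFR) above 13 mL/kg/h"; 13 mL/kg/h allows 13 × 3 = 39 mL/kg (3.9%) in 3 h, 5.2% in 4 h and 7.8% in 6 h.

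**Sign of the fluid term.** 4 − 3.5R = 0 at R = 4/3.5 = 1.143. With R = pre/post = 1/(1 − URR), that is URR = 1 − 3.5/4 = 12.5%. At URR 65%:

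- R = pre/post = 1/0.35 = 2.857, coefficient 4 − 10 = −6.0
- R = post/pre = 0.35, coefficient 4 − 1.225 = +2.775

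Each extra 1% of body weight removed therefore changes Kt/V by −0.06 as written and by +0.03 in the consistent form.

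**All four readings** at URR 65%, t = 4 h, f = 3%:

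| Log sign | R | Log part | Fluid part | Kt/V |
|---|---|---|---|---|
| + (as written) | pre/post | ln(2.857 − 0.032) = 1.039 | −6.0 × 0.03 = −0.180 | 0.859 |
| + | post/pre | ln(0.35 − 0.032) = −1.146 | 2.775 × 0.03 = +0.083 | −1.062 |
| − | pre/post | −1.039 | −0.180 | −1.219 |
| − | post/pre | +1.146 | +0.083 | 1.229 |

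Only the last agrees with the paired thresholds. Correcting the sign alone or the ratio alone gives a negative Kt/V.

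**Size over the grid** (t = 3, 4, 5, 6 h; f = 0 to 5%):

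| URR | As written | Consistent form |
|---|---|---|
| 65% | 0.73 to 1.04 | 1.12 to 1.34 |
| 70% | 0.81 to 1.197 | 1.29 to 1.53 |
| 75% | 0.87 to 1.38 | 1.49 to 1.76 |

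The largest value as written at URR 70% is 1.197 (t = 3 h, f = 0), still under 1.2.

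**URR at which Kt/V reaches 1.2, t = 4 h:**

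| f | As written | Consistent form |
|---|---|---|
| 0 | 70.2% | 66.7% |
| 1% | 72.7% | 65.8% |
| 2% | 75.7% | 65.0% |
| 3% | 80.1% | 64.1% |

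The consistent column lies close to the plan's 65%; the other does not.

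**Flow-rate contrast** at equal URR and equal f, 5 h minus 3.5 h: −0.004 as written against +0.038 at URR 65%, and −0.003 against +0.056 at URR 75%.

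**Independent check.** A single-pool, variable-volume urea mass balance was simulated with a known true Kt/V (assumed: V = 35 L, generation 6 mg/min, starting urea nitrogen 700 mg/L). The consistent form returned 1.18 to 1.19 for a true 1.2, 1.40 for 1.4, and 1.61 to 1.62 for 1.6. For a true 1.4 at 3.5 h, the text as written returned 1.29, 1.03 and 0.82 as UF rose from 0 to 1.5 to 3 L.

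**Height slip.** Dividing by 2.54 instead of multiplying makes height in cm too small by 2.54² and BMI too large by 2.54⁴ = 41.6. For 67 in and 80 kg, BMI is 1,150 instead of 27.6 kg/m².

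**The case against.** The strongest objection is that the equation comes from a damaged PDF: the log is misprinted, so a leading minus could have been lost too. If the original has the minus, the as-written figures above do not apply. The only error is then one phrase, pre/post for post/pre, and literal use gives about −1.22 at URR 65%, which would be caught on the first run. This limits confidence in the size of the error but not in the mismatch: R in words fits the equation under neither sign, and with the minus restored Kt/V still falls as fluid removal rises.

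Other points that stand in part:

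- The statement about URR 65 to 70% needs fluid removal of zero or more. At URR 70%, 3 h and a net gain of 0.1% of body weight, the value is 1.204. The SAP plans no count of sessions below 1.2, and the documents give no URR distribution, so the number of sessions affected is unknown.
- The flow-rate distortion from session length alone is small: 0.042 at URR 65% and 0.059 at URR 75%. The larger error comes through fluid removal, and nothing in the documents shows that this differs systematically by flow rate.
- The cited formula and the correctly defined URR give a programmer two chances to notice. They make it less likely that the error reaches the results but leave the text wrong.
- V has no named method, so correcting R and the sign does not by itself make Kt/V reproducible.

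**Conclusion.** The point holds. The definition of R in SAP 4.8.1 is incompatible with the equation it feeds, whichever sign stands before the log. Taken as written, Kt/V at URR 65% is 0.73 to 1.04 where a consistent calculation gives 1.12 to 1.34, and it moves the wrong way with fluid removal.

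The direction follows from the sign of (4 − 3.5R) and the SAP's own URR formula. The size rests on the assumed 0 to 5% fluid removal, on V being 55% of body weight, and on the original SAP having no minus sign.

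The main harm is the level of the reported values; the session-length effect on the flow-rate contrast is secondary. The consequence is limited to a descriptive secondary endpoint, and the documents do not show sites using this equation for run-in decisions. It should be corrected before programming. The inches conversion is a separate minor error that would expose itself against the 18 to 37 kg/m² entry range.

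**What to change.** Correct ratio and sign together in SAP 4.8.1:

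- R = post-dialysis BUN / pre-dialysis BUN
- Kt/V = −ln(R − 0.008 × t) + (4 − 3.5 × R) × 0.55 × UF/V, with t in hours and UF and V both in litres

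Before programming, check this against the cited publication and the original SAP file, since the minus sign may already be there. State in the same place which method supplies V.

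Add a programming check over t = 3 to 6 h and f = 0 to 5%: URR 65% must return 1.12 to 1.34, URR 70% must return 1.29 to 1.53, and Kt/V must rise with fluid removal. These ranges come from the proposed equation, so they test the code; the publication is the test of the equation.

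Separately, in SAP 4.4.1, convert inches to cm by multiplying by 2.54.

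The cost is two text corrections, a line on V and one programming check. Kt/V is computed from data already collected, so no data change is needed.
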